## 6 STUDY PERIODS, TREATMENT REGIMENS AND POPULATIONS FOR ANALYSES

### 6.1 Study Periods

#### NIVOLUMAB MONOTHERAPY COHORTS

This study consists of Screening (up to 28 days), Treatment (up to 2 years), Clinical Follow-up (up to 12 months) and Survival Follow-up (up to 2 years). There is also the possibility of Retreatment (up to 1 year) and Follow up (up to 120 days).

#### IPILIMUMAB/NIVOLUMAB COHORTS

The study will consist of Screening (up to 28 days), Treatment (up to 2 years), and Follow-up.

#### LIRILUMAB/NIVOLUMAB COHORTS

The study will consist of Screening (up to 28 days), Treatment (up to 2 years), and Follow-up.

#### NIVOLUMAB/DARATUMUMAB COHORTS

The study will consist of Screening (up to 28 days), Treatment (until disease progression), and Follow-up.

### 6.2 Treatment Regimens

**Table 2: Treatment Information**

Regimen	Specification
Nivolumab	Nivo 1
Nivolumab	Nivo 3
Nivolumab + Ipilimumab	Nivo 3 + Ipi 1
Nivolumab + Lirilumab	Nivo 3 + Liri 3
Cohort A	
Nivolumab + Daratumumab + Pomalidomide + Dexamethasone	Nivo + Dara + Pom + Dex
Nivolumab + Daratumumab	Nivo + Dara
Cohort B	
Nivolumab + Daratumumab	Nivo+Dara
Daratumumab	Dara

### 6.3 Populations for Analyses

- All Enrolled Subjects: All subjects who sign informed consent form and were registered in IVRS.
- All Randomized MM subjects: All enrolled MM subjects who were randomized to one of nivolumab and daratumumab cohorts.
- All Treated Subjects: All subjects who signed informed consent and received at least one dose of study medication are considered treated and are included in the treated population
- Pharmacokinetic (PK) Population: All subjects who receive at least one dose of study medication and have available serum concentration data.
- Response Evaluable Subjects: All treated subjects with measurable disease at baseline and one of the following: 1) at least one on-treatment efficacy assessment, 2) clinical progression, or 3) death.
- Immunogenicity evaluable subjects:
  - Nivolumab ADA Evaluable Subjects: all treated subjects with baseline and at least 1 postbaseline nivolumab immunogenicity assessment.
  - Ipilimumab ADA Evaluable Subjects: all treated subjects with baseline and at least 1 postbaseline Ipilimumab immunogenicity assessment.
  - Lirilumab ADA Evaluable Subjects: all treated subjects with baseline and at least 1 postbaseline Lirilumab immunogenicity assessment.
- All Treated PD-L1 Evaluable Subjects: All treated subjects with quantifiable PD-L1 expression (ie excludes indeterminate and unknown).
- All MRD Evaluable Subjects: All subjects in Cohorts A and B with available MRD status data.

## 7 STATISTICAL ANALYSES

### 7.1 General Methods

All analysis will be performed in SAS using version 8.2 or higher. Some figures will be generated using S-Plus.

Continuous variables will be summarized using descriptive statistics, i.e. medians, minimums, maximums and means with standard deviations. Categorical variables will be summarized by frequencies and percents. Percentages will be rounded and, therefore, may not always add up to 100.

Unless specified otherwise, analyses will be performed by disease type within each treatment group.

### 7.2 Study Conduct

#### 7.2.1 *Accrual*

Number (%) of subjects accrued by country and investigational site will be presented on the all enrolled subjects. The corresponding listing will be provided.

### **7.2.2 Protocol Deviation**

Deviation from protocol inclusion and exclusion criteria will be listed for all treated subjects for nivolumab monotherapy cohorts, nivolumab/lirilumab cohorts, nivolumab/Ipilimumab cohorts and all randomized MM subjects for nivolumab/daratumumab cohorts.

## **7.3 Study Population**

### **7.3.1 Subject Disposition**

The number of subjects enrolled into the study, the number of subjects entering the treatment period or the number of subjects randomized and the number of subjects enrolled but not randomized/treated together with the reasons for not being dosed will be summarized.

The number of treated subjects, the number of subjects discontinuing during treatment period along with the reasons for discontinuation, and the number of subjects continued to be followed after discontinuing will be summarized by dose level or by treatment arm for nivolumab/daratumumab cohorts.

All related data will be listed.

### **7.3.2 Demographics and Other Baseline Characteristics**

Subject demographics and baseline characteristics will be summarized for all treated subjects for nivolumab monotherapy cohorts, nivolumab/lirilumab cohorts, nivolumab/Ipilimumab cohorts and all randomized MM subjects for nivolumab/daratumumab cohorts.

Demographic characteristics include age in years, age category (<65 vs.  $\geq 65$ ;  $\geq 75$ ), gender, race, ethnicity, ECOG, and weight.

Baseline characteristics include: baseline disease characteristics (disease diagnosis, stage), prior therapy surgery, radiotherapy and systemic cancer therapy), general medical history, and baseline cytogenetic status.

For multiple myeloma subjects, baseline disease characteristics include time to study entry from disease diagnosis, ISS stage, IMWG risk stage, prior systemic cancer therapy, prior ASCT, refractoriness to prior therapies (i.e., IMiD, PI, last treatment), type of measurable disease, percentage bone marrow plasma cells, general medical history, and cytogenetic profile at study entry.

The risk factors for potential events such as pulmonary related events will be listed by dose levels for nivolumab monotherapy cohort.

All related data will be listed.

### **7.3.3 Prior Anti-Cancer Therapy**

For non-nivolumab/daratumumab cohorts, the following will be summarized: 1. by disease type and treatment arms, 2. by prior ASCT (subjects who were treated with prior ASCT) and ASCT

naive (subjects who weren't treated with prior ASCT) within disease type and treatment arms, and 3. by Responders vs. Non-Responders.

- Number of prior regimens
- Best response to prior systemic therapy
- Best response to the most recent prior systemic therapy
- Time from completion of the most recent prior regimen to the 1st dose of study medication

For nivolumab-daratumumab cohorts, refractoriness to prior anti-myeloma therapy is defined as progression that occurred on treatment or within 60 days of the last dose of the respective prior treatment. A subject will not be considered as refractory to a prior therapy if the date of progression to the respective prior treatment is missing. Missing/partial dates will be imputed according to the rule in Section 8.

For nivolumab/daratumumab cohorts, the following will be derived and summarized:

- Number of prior regimens
- Refractory to a IMiD
- Refractory to Proteasome Inhibitor (PI)
- Refractory to both IMiD and PI
- Refractory to most recent prior therapy

IMiD includes lenalidomide, thalidomide, and pomalidomide. PI includes bortezomib, carfilzomib, and ixazomib. Refractory status to PI or IMiD will be derived for subjects who received at least two consecutive cycles (2 months) of PI or IMiD,

## **7.4 Extent of Exposure**

Summaries of exposure will be based on all treated subjects.

### **7.4.1 Study Therapy**

For nivolumab, ipilimumab, lirilumab, daratumumab, pomalidomide and dexamethasone, the following parameters will be listed and summarized.

- Number of doses
- Duration of therapy
- Cumulative dose per subject
- Dose intensity per subject (/week)
- Relative dose intensity per subject

Cumulative dose (mg/kg) is defined as: the sum over the duration of the study of all delivered doses (mg/kg) per subject.

Dose intensity per subject (/week) is calculated as the cumulative dose (mg/kg) divided by the duration of therapy (weeks).

Relative dose intensity is defined as dose intensity divided by planned dose per week (relative dose (%) = dose intensity / planned dose per week) \* 100).

Duration of therapy (weeks) is defined as: (last dose date - first dose date + 1)/7.

A listing of study drug administered will be provided. Duration of therapy, cumulative dose, dose intensity and relative dose intensity of relative study drugs will be listed. A listing of study medication by batch (or vial) number will be provided.

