4.1.4.2 Daratumumab

Daratumumab will be administered at a dose of 16 mg/kg as an IV infusion every week (Days 1, 8, 15, and 22 of each 28-day cycle) during Cycles 1 and 2. As an option, in Cycle 1, the first full dose of daratumumab at 16 mg/kg may be split into 2 doses at 8 mg/kg and administered via IV on Cycle 1 Days 1 and 2. From Cycles 3 through 6, daratumumab will be administered every 2 weeks (Days 1 and 15 of each 28-day cycle), then starting Cycle 7 and beyond, daratumumab will be administered every 4 weeks (Day 1 of each 28-day cycle). The infusion rates should closely follow the specifications of the currently approved (USPI)/pharmacy reference manual.⁹⁸

All infusions will be planned as outpatient visits. Subjects will receive preinfusion medications and postinfusion medications as detailed in the protocol.

Daratumumab should be administered after nivolumab.

MM subjects randomized to the ND or D regimens will receive pre- and post-infusion medication for daratumumab infusion per the daratumumab label, as described (in [Section 3.4.1.4](#)).

MM subjects randomized to ND-Pd regimen will receive the treatment regimen dexamethasone dose split as IV pre-infusion and oral post-infusion on weeks with daratumumab infusions, and only oral in the weeks without daratumumab infusion (see [Section 4.1.4.4](#)). No additional corticosteroids besides the dexamethasone dose included in the treatment regimen will be administered to the ND-Pd subjects.

The dilution volumes and infusion rates for C1D1 (16 mg/kg), and optional split-dosing of C1D1 (8 mg/kg) and C1D2 (8 mg/kg), C1D8 (16 mg/kg), and subsequent infusions are provided in [Table 4.1.4.2-1](#). The sponsor may modify the infusion rates or the preinfusion medications prospectively based upon the information collected to date from this and other studies. Additional details for administration times and rates, as well as preinfusion medications, will be provided in the administration guidelines (study site investigational product and procedures manual/package insert).

Table 4.1.4.2-1: Daratumumab Infusion Rates

	Dilution Volume	Initial Infusion Rate (first hour)	Increments of Infusion Rate	Maximum Infusion Rate
C1D1 (16 mg/kg single dose)	1000 mL	50 mL/hour	50 mL/hour every hour	200 mL/hour
Optional split-dosing: C1D1 and C1D2 (8 mg/kg split dose)	500 mL	50 mL/hour	50 mL/hour every hour	200 mL/hour

Table 4.1.4.2-1: Daratumumab Infusion Rates

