4.1.4.3 Pomalidomide in the ND-Pd Cohort (Cohort A)

Pomalidomide will be administered orally at the dose of 4 mg daily on Days 1 - 21 of each 28-day cycle. Pomalidomide should be taken without food (at least 2 hours before or 2 hours after a meal).

Subjects should be instructed that if a dose of pomalidomide has been missed and it has been less than 12 hours since the subject's regular dosing time, to take pomalidomide as soon as the subject remembers. If it has been more than 12 hours, the dose must be skipped. Subjects should not take 2 doses at the same time.

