4.1.5 Dose Delay, Interruption, or Discontinuation

If the dose of nivolumab, daratumumab, pomalidomide and/or dexamethasone is interrupted or discontinued, the treatment with the other drugs may continue as scheduled if deemed in their

best interest by both the PI and the BMS medical monitor. Subjects must be deriving clinical benefit.

Each cycle is 28 days. While dose delays (within the allowed window determined below for nivolumab and daratumumab) or interruptions are permitted, the start of each cycle cannot be delayed and is fixed (ie, anchored) relative to Cycle 1 Day 1. Adjustments to the Cycle 1 Day 1 anchored schedule should not be performed. Should the start of a cycle be delayed, it is expected the following cycle begin as anchored to Cycle 1 Day 1. Delayed doses which fall outside of the allowed window for delay for the respective cycle should be skipped. Subjects may continue on study therapy even if components of the study therapy must be discontinued.

Please consult the BMS Medical Monitor or any questions regarding dose interruption or study therapy discontinuation.

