4.1.5.1 Nivolumab

Cohort A

During Cycles 1 through 6, subjects may be dosed no less than 12 days from the previous dose. Nivolumab can be delayed within a 3-day window of Day 1 and Day 15 as long as the 12-day interval between 2 nivolumab 240 mg doses is respected. Doses that fall outside the allowed window should be skipped.

The first dose in Cycle 7 (Day 1) may be dosed no less than 12 days from the previous dose and for subsequent doses it should be dosed no less than 21 days from the previous dose. From Cycle 7 and beyond, nivolumab can be delayed within a 7-day window of Day 1 as long as the 12-day and 21-day intervals for the first 480 mg dose and subsequent 480 mg doses, respectively, between 2 nivolumab doses is respected. Doses that fall outside the allowed window should be skipped.

Cohort B

Cycle 1 dose (C1D15) can be delayed within a 3 day window from Day 15. Doses that fall outside the allowed window should be skipped.

From Cycle 2 (C2D1) and beyond, nivolumab can be delayed within a 7 day window from Day 1, as long as the 21-day interval between two 480 mg nivolumab doses is respected, and a 12-day interval between C1D15 and C2D1 is respected. . Doses that fall outside the allowed window should be skipped.

Nivolumab Dose Delays Due to AEs

Nivolumab administration should be delayed for the following:

- Grade 2 non-skin, drug-related AE, with the exception of fatigue
- Grade 2 drug-related creatinine, AST, ALT and/or Total Bilirubin abnormalities
- Grade 3 skin, drug-related AE
- Grade 3 drug-related laboratory abnormality, with the following exceptions:
 - Grade 3 lymphopenia or asymptomatic amylase or lipase does not require dose delay

- Grade ≥ 3 AST, ALT, Total Bilirubin will require dose discontinuation
- Any adverse event, laboratory abnormality, or intercurrent illness which, in the judgment of the investigator, warrants delaying the dose of study medication.

Participants who require delay of nivolumab should be re-evaluated weekly or more frequently if clinically indicated and resume nivolumab dosing when re-treatment criteria are met.

Criteria to Resume Treatment with Nivolumab

In order to initiate a new infusion of nivolumab the following criteria must be met:

- Platelet count $\geq 25 \times 10^9/L$ (platelet transfusion support is allowed)
- ANC $\geq 0.50 \times 10^9/L$ (growth factor support is strongly recommended if ANC $< 1.0 \times 10^9/L$)

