For subjects in Cohort B, those randomized to ND treatment will receive nivolumab at a dose of 240 mg as an intravenous infusion over 30 minutes on Day 15 of Cycle 1. Starting Cycle 2 and beyond, nivolumab will be administered at a dose of 480 mg as an intravenous infusion over 30 minutes every 4 weeks (Day 1 of each 28 day cycle). Daratumumab will be administered at a dose of 16 mg/kg as an IV infusion every week (Days 1, 8, 15, and 22 of each 28-day cycle) during Cycles 1 and 2. During Cycles 3 through 6 daratumumab will be administered every 2

weeks (Days 1 and 15 of each 28-day cycle), then starting Cycle 7 and beyond, daratumumab will be administered every 4 weeks (Day 1 of each 28-day cycle).

Nivolumab should be administered before daratumumab on the days when both nivolumab and daratumumab are administered.

After informed consent has been obtained, the subject must be enrolled into the study by calling an interactive voice response system (IVRS) to obtain the subject number.

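### SAP 7.4.1 counts the last dose in full but gives it one day, so dose intensity of nivolumab and daratumumab is overstated, and the planned dose per week has no stated time basis

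*SAP*

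**What the plan says.** SAP 7.4.1 lists number of doses, duration of therapy, cumulative dose, dose intensity and relative dose intensity for nivolumab, ipilimumab, lirilumab, daratumumab, pomalidomide and dexamethasone. Duration is fixed by one rule for all of them: "Duration of therapy (weeks) is defined as: (last dose date - first dose date + 1)/7". Dose intensity is the cumulative dose divided by that duration, and the cumulative dose is expressed in mg/kg. For the last parameter the section says "Relative dose intensity is defined as dose intensity divided by planned dose per week". No value, formula or time basis for the planned dose follows.

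The schedules to which this applies are spelled out. Under SAP 2.2, Cohort B subjects in the combination arm receive "nivolumab at a dose of 240 mg as an intravenous infusion over 30 minutes on Day 15 of Cycle 1" and then 480 mg on Day 1 of each 28-day cycle from Cycle 2. Daratumumab (Protocol 4.1.4.2) is 16 mg/kg weekly in Cycles 1 and 2, every 2 weeks in Cycles 3 to 6 and every 4 weeks after that. Pomalidomide in Cohort A is given "orally at the dose of 4 mg daily on Days 1 - 21 of each 28-day cycle" (Protocol 4.1.4.3).

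Doses can be lost from the middle of a course. Protocol 4.1.5 states that "the start of each cycle cannot be delayed and is fixed (ie, anchored) relative to Cycle 1 Day 1", and for nivolumab Protocol 4.1.5.1 adds: "Doses that fall outside the allowed window should be skipped".

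**The concern.** A dose given every 4 weeks covers 28 days of treatment. The duration rule gives the last such dose a single day while the numerator keeps all of it. The shortfall in time is fixed (27 days for a 28-day interval), so its relative effect is greatest when the course is short. Subjects who stop early, often those who tolerate treatment least, get the highest dose intensity. SAP 7.1 summarises continuous variables with means, standard deviations and maximums, so a few such subjects can pull an arm's summary upward.

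Relative dose intensity inherits the problem and adds an undefined denominator. Two programmers could each follow SAP 7.4.1 and report different percentages for the same subject. On one natural reading a missed interior dose almost disappears from the percentage.

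**Working it through.** The plan states no dose-intensity figure, so there is nothing to reproduce. The check applies the formulas of SAP 7.4.1 to the protocol schedule.

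**Inputs, Cohort B nivolumab** (SAP 2.2; 28-day cycles anchored to Cycle 1 Day 1). Doses fall on study day 15 (240 mg) and on days 29, 57, 85, 113 and 141 (480 mg each) through Cycle 6. The scheduled rate is 240 mg over 2 weeks, then 480 mg over 4 weeks, which is 120 mg/week throughout. That rate is inferred from the schedule; the SAP does not give it.

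**Dose intensity as written, on schedule through Cycle 6**
- Cumulative dose: 240 + 5 × 480 = 2640 mg.
- Duration: (141 − 15 + 1)/7 = 127/7 = 18.14 weeks.
- Dose intensity: 2640/(127/7) = 145.5 mg/week.

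**The same rule for other course lengths, every dose on schedule**

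| Last dose | Cumulative mg | Duration (weeks) | Dose intensity (mg/week) | Relative to 120 |
|---|---|---|---|---|
| Cycle 1 | 240 | 1/7 | 1680 | 1400% |
| Cycle 2 | 720 | 15/7 | 336 | 280% |
| Cycle 4 | 1680 | 71/7 | 165.6 | 138.0% |
| Cycle 6 | 2640 | 127/7 | 145.5 | 121.3% |
| Cycle 13 | 6000 | 323/7 | 130.0 | 108.4% |

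**One interior 480 mg dose skipped, last dose still in Cycle 6**
- Dose intensity: 2160/(127/7) = 119.1 mg/week.
- Drug delivered: 2160/2640 = 81.8% of schedule.
- Against 120 mg/week: 99.2%. The lost dose is worth 28 days at the scheduled rate and the duration is 27 days short, so the two nearly cancel.
- Against a plan over the same first-to-last-dose span, 2640/(127/7) = 145.5 mg/week: 81.8%, with the on-schedule subject at 100%.

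**Daratumumab, 16 on-schedule doses through Cycle 6** (last on day 155)
- Dose intensity: 256/(155/7) = 11.56 mg/kg/week.
- Scheduled rate, time-weighted over the same 155 days: (56 × 16 + 99 × 8)/155 = 10.89 mg/kg/week.
- Relative dose intensity: 11.56/10.89 = 106.2%.

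**With the last dose given its scheduled interval**
- Nivolumab: (141 − 15 + 28)/7 = 22 weeks. On schedule, 2640/22 = 120 mg/week (100%). One interior skip, 2160/22 = 98.2 mg/week (81.8%).
- Daratumumab: (155 − 1 + 14)/7 = 24 weeks. 256/24 = 10.67 mg/kg/week, against a plan of (56 × 16 + 112 × 8)/168 = 10.67 (100%).
- Last nivolumab dose 7 days late (day 148): (148 − 15 + 28)/7 = 23 weeks; 2640/23/120 = 95.7%.
- First nivolumab dose 3 days late (day 18): (141 − 18 + 28)/7 = 151/7 weeks; 2640/(151/7)/120 = 102.0%. The 12-day minimum then moves the Cycle 2 dose to day 30, which leaves the span unchanged.
- Final (Cycle 6) dose skipped, last dose on day 113: (113 − 15 + 28)/7 = 18 weeks; 2160/18/120 = 100%. The present rule gives 2160/(99/7)/120 = 127.3%.

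**The case against.** The strongest reply is that the percentages rest on a planned rate that the SAP never states. If the plan is taken over the same first-to-last-dose span, relative dose intensity comes out right. Adding one day is also an ordinary way to count duration. The measure is descriptive, and missed doses stay visible in the number of doses, the cumulative dose and the dosing listing of SAP 7.4.1, and in the omissions, delays and discontinuations of SAP 7.4.2. The mg/kg wording is a matter of labelling, since a ratio is unaffected when numerator and plan share a unit.

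Most of this stands. The 121.3% and 99.2% are conditional on 120 mg/week, and the consequence is limited. What the reply does not reach is dose intensity itself, which SAP 7.4.1 fully defines: 145.5 and 1680 mg/week follow whatever the planned dose means. A sponsor standard might define the planned dose, but SAP 7.4.1 does not point to one, whereas most of SAP 7.6 refers to the Core Safety SAP.

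Three stronger inferences are tempting and are not supported:
- A reader might conclude that relative dose intensity is simply wrong. It is undetermined; one admissible reading is correct.
- A reader might widen the range with a fixed 16 mg/kg/week for daratumumab, 28 mg/week for pomalidomide, or a nivolumab clock that starts on Cycle 1 Day 1. The first two ignore the stepped and 21-of-28-day schedules. The third ignores that SAP 7.4.1 applies its parameters drug by drug.
- A reader might infer that the tolerability conclusions are compromised. No primary endpoint, stopping rule or interim analysis in the visible text uses this measure.

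**Conclusion.** The concern holds for descriptive exposure reporting. As written, dose intensity of the interval-dosed antibodies is too high: 145.5 instead of 120 mg/week for on-schedule Cohort B nivolumab through Cycle 6, and 1680 mg/week for a subject with only the first dose. The excess shrinks as treatment lengthens. This part assumes only the protocol schedule and drug-specific first and last dose dates.

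Relative dose intensity is not determined by the text. Through Cycle 6 it reads 121.3% (on schedule) and 99.2% (one interior skip) against an assumed 120 mg/week, or 100% and 81.8% against a same-span plan. Daratumumab reads 106.2% for full compliance against a time-weighted rate. The point merits correction because tolerability is the primary objective and the data needed are already collected, but it does not bear on any decision rule.

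**What to change.** Amend SAP 7.4.1 as follows.
- Keep the present formula for the reported duration of therapy, and state that first and last dose dates are taken per drug.
- For dose intensity and relative dose intensity of nivolumab and daratumumab, use (last dose date − first dose date + scheduled interval of the last dose in days)/7.
- Define planned dose per week for each drug as the protocol-scheduled dose over the same period divided by its weeks. For the antibodies this is the scheduled weekly rate, time-weighted over the period. For pomalidomide, use the scheduled dosing days within its first-to-last-dose span, so that the off-week is handled. Dexamethasone needs its own line, because its scheduled dose depends on age and the oral dose may be split over 2 days.
- Report flat-dosed drugs in mg and weight-based drugs in mg/kg.

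The change is one of wording and programming on existing data. Its costs should be stated in the SAP. Antibody dose intensity will be reported lower and will no longer equal cumulative dose over the reported duration. Permitted delays will move relative dose intensity a few percent from 100% (about 96% to 102% for nivolumab through Cycle 6). A skipped final dose or an early stop will still read 100% and must be read from the dose-omission and discontinuation tables.

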Subjects should discontinue study therapy upon evidence of further progression, defined as an additional 10% or greater increase in tumor burden volume from the time of initial progression (including all target lesions and new measurable lesions) or similar criteria in tumor types without measurable lesions.

Subjects who experience AEs that require discontinuation while receiving both nivolumab and ipilimumab may be allowed to continue therapy with nivolumab only, if deemed in their best interest by both the PI and the BMS medical monitor. Subjects must be deriving clinical benefit.

Subjects who experience AEs that require discontinuation while receiving both nivolumab and lirilumab may be allowed to continue therapy with nivolumab only, if deemed in their best interest by both the PI and the BMS medical monitor. Subjects must be deriving clinical benefit.

Re-initiation of Study Therapy for Subjects in Follow-up Period

Subjects entering the follow-up period with ongoing disease control (ongoing CR, PR, or SD) may reinitiate study therapy upon confirmed disease progression after discussion and agreement with the BMS Medical Monitor. Subjects reinitiating study therapy should continue to meet eligibility criteria at the time study drug resumes and should not have experienced a DLT requiring permanent discontinuation of study therapy. Subjects will receive study therapy at the same dose level that they received prior to entering the follow-up period. Subjects that resume study therapy in this setting may receive study therapy for up to one additional year. Subjects who have completed 1 year of follow-up without evidence of disease progression will not be considered eligible for re-initiation of study therapy. Additional safety and efficacy summaries will be presented for those subjects who reinitiated study therapy.

IPILIMUMAB/NIVOLUMAB COHORTS

Subjects enrolled in the nivolumab and ipilimumab combination cohorts will not be eligible for re-initiation of study therapy for progression in the follow-up period.

LIRILUMAB/NIVOLUMAB COHORTS

Subjects enrolled in the nivolumab and lirilumab combination cohorts will not be eligible for re-initiation of study therapy for progression in the follow-up period.

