#### **NIVOLUMAB MONOTHERAPY COHORTS**

These monotherapy cohorts will consist of Screening (up to 28 days), Treatment (up to 2 years), and Clinical Follow-up (up to 12 months) and Survival Follow-up (up to 2 years). There is also the possibility of Retreatment (up to 1 year) and Follow up (up to 120 days). The first dose administered will be followed by a three-week period for pharmacokinetic and pharmacodynamic assessment of nivolumab. A response assessment following administration of the first dose will be obtained. Therapy will be given on an every two week schedule thereafter with response assessments performed at Weeks 8, 16, 24 and then every 16 weeks thereafter. The scheduled response assessments must be completed before the next dose of therapy.

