## 2.2 Treatment Assignment

For patients receiving monotherapy nivolumab, nivolumab will be administered as an IV infusion on treatment day 1 followed by a 3 week interval to evaluate pharmacokinetics and duration of pharmacodynamics effects and then every two weeks for up to 2 years. Two dose levels will be explored, 1 mg/kg or 3 mg/kg, which will be administered at Week 1 and Week 3, then every 2 weeks. Therapy will be continued for up to 2 years with the potential for one additional year of therapy for retreatment eligible subjects in follow up.

For patients receiving nivolumab in combination with ipilimumab therapy, nivolumab at 3 mg/kg and ipilimumab at 1 mg/kg will be administered every three weeks for four doses followed by nivolumab alone at 3 mg/kg every 2 weeks for a total of two years of therapy.

For patients receiving nivolumab in combination with lirilumab therapy, nivolumab 3 mg/kg will be administered every 2 weeks, and lirilumab 3 mg/kg will be administered every 4 weeks for a total of two years of therapy.

For subjects in Cohort A, nivolumab will be administered at a dose of 240 mg as an intravenous infusion over 30 minutes on Day 15 during Cycle 1, and on Days 1 and 15 during Cycles 2 through 6 (ie, every 2 weeks of each 28-day cycle). Starting Cycle 7 and beyond, nivolumab will be administered at a dose of 480 mg as an IV infusion over 30 minutes every 4 weeks (Day 1 of each 28-day cycle). Daratumumab will be administered at a dose of 16 mg/kg as an IV infusion every week (Days 1, 8, 15, and 22 of each 28-day cycle) during Cycles 1 and 2. During Cycles 3 through 6 daratumumab will be administered every 2 weeks (Days 1 and 15 of each 28-day cycle), then starting Cycle 7 and beyond, daratumumab will be administered every 4 weeks (Day 1 of each 28-day cycle). Pomalidomide in the ND-Pd treatment arm will be administered orally at the dose of 4 mg daily on Days 1 - 21 of each 28-day cycle. Dexamethasone in the ND-Pd treatment arm will be administered as described in section 4.1.4.4. of the protocol.

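### SAP 7.4.1 counts the planned off-drug gap of retreated monotherapy subjects as time on therapy, so their dose intensity is understated: by about 25% with every period at its maximum

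*SAP*

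**What the plan says.** SAP 7.4.1 (Study Therapy) defines cumulative dose as "the sum over the duration of the study of all delivered doses (mg/kg) per subject". Duration is one span: "Duration of therapy (weeks) is defined as: (last dose date - first dose date + 1)/7". Dose intensity is the first divided by the second, and relative dose intensity divides that by the planned weekly dose. SAP 7.4 applies these summaries to all treated subjects.

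The monotherapy design allows two courses. SAP 2.2 (Treatment Assignment) says: "Therapy will be continued for up to 2 years with the potential for one additional year of therapy". SAP 2.1 and 6.1 list treatment, clinical follow-up of up to 12 months and retreatment as distinct periods. In the protocol version revised 01-Oct-2015, Section 3.1.2 lets subjects with ongoing CR, PR or SD restart at the same dose level on confirmed progression during follow-up: "Subjects that resume study therapy in this setting may receive study therapy for up to one additional year". The same section limits the gap: "Subjects who have completed 1 year of follow-up without evidence of disease progression will not be considered eligible for re-initiation of study therapy".

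**The concern.** A first-to-last-dose span suits one continuous course. A retreated monotherapy subject has two courses with a planned interval between them in which no drug is due. Under SAP 7.4.1 that interval counts as time on therapy, although the doses on both sides of it are summed.

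A subject who received every planned dose in both courses would thus be listed with a duration inflated by the whole gap and a relative dose intensity well below 100%. A reader of the exposure table or listing could take this for missed or delayed dosing when none occurred.

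**Working it through.** The documents state no dose-intensity figure, so there is nothing to reproduce. The check applies the SAP formula to a fully compliant subject.

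**Inputs from the documents**
- First course at most 2 years (104 weeks); retreatment at most 1 year (52 weeks): SAP 2.2.
- Off-drug gap at most about 1 year (52 weeks): protocol 3.1.2, revised 01-Oct-2015.
- Second dose 3 weeks after the first, then every 2 weeks: SAP 2.2 and the synopsis of the same protocol version.
- Dose 3 mg/kg, unchanged on retreatment.

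**Assumptions**
- All doses given, with a 2-week interval on retreatment.
- Planned rate 3/2 = 1.5 mg/kg/week. This cancels out of the percentage understatement.
- Gap measured from the last dose of course 1 to the first dose of course 2.

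**All periods at their maxima (104 on, 52 off, 52 on)**
1. Course 1: doses on days 0, 21, 35, …, 721, which is 52 doses.
2. Course 2: starts on day 721 + 364 = 1085 and runs every 14 days to day 1435, which is 26 doses.
3. Cumulative dose: 78 × 3 = 234 mg/kg.
4. SAP duration: (1435 − 0 + 1)/7 = 205.1 weeks.
5. On-drug duration: (721 − 0 + 1)/7 + (1435 − 1085 + 1)/7 = 103.1 + 50.1 = 153.3 weeks (before rounding).
6. SAP dose intensity: 234/205.1 = 1.141 mg/kg/week; relative dose intensity 1.141/1.5 = 76.0%.
7. On-drug dose intensity: 234/153.3 = 1.527 mg/kg/week; relative dose intensity 101.8%.
8. Understatement: 1 − 1.141/1.527 = 25.3%. The simple gap share, 52/(104 + 52 + 52), gives 25.0%.
9. The on-drug figure exceeds 100% because the formula leaves out the last dosing interval of each course. Counting 14 days after each course's last dose gives (735 + 364)/7 = 157.0 on-drug weeks, and the understatement becomes 1 − 157.0/205.1 = 23.5%.

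**Other lengths within the maxima** (illustrative; the documents give no typical values)

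| Weeks on / off / on | Relative dose intensity by SAP formula | Understatement | With last interval of each course counted |
|---|---|---|---|
| 104 / 4 / 52 | 99.3% | 2.5% | 0.1% |
| 104 / 13 / 52 | 93.9% | 7.7% | 5.5% |
| 104 / 26 / 52 | 87.1% | 14.4% | 12.4% |
| 104 / 52 / 52 | 76.0% | 25.3% | 23.5% |
| 52 / 52 / 52 | 67.9% | 33.9% | 31.4% |
| 26 / 52 / 52 | 61.3% | 40.8% | 37.9% |

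For comparison, a subject with one uninterrupted 104-week course and no retreatment reads 100.8%. The formula behaves as intended there.

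**The case against.** **Reach.** Only monotherapy subjects can be affected. The ipilimumab and lirilumab combination cohorts may not re-initiate (protocol 3.1.2, revised 01-Oct-2015), and the daratumumab cohorts receive no study therapy after confirmed progression (current protocol 4.1.7). SAP 2.4 records that Amendment 15 removed the monotherapy cohort from the protocol. All this stands, but SAP version 3.2 still describes that cohort and applies 7.4.1 to it.

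**Consequence.** Number of doses and cumulative dose are not distorted. The drug administration listing would show a long gap, and SAP 7.4.2 reports delays and discontinuations with reasons. Medians would move little if few subjects were retreated. This limits the harm, but the derived values would still be wrong for those subjects.

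**Another reading of the formula.** If the last dose date meant the end of the initial course, the gap would drop out, but the retreatment doses would stay in the numerator: 234/103.1 = 2.269 mg/kg/week, or about 151% of plan. Numerator and denominator do not match on either reading.

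**Unseen text.** Text after SAP 7.4.2 is redacted, and the sponsor's standard counting rules (SAP 8) and the core safety SAP are not available. A course-specific rule there cannot be excluded. The readable text has none, and the extra summaries promised for re-initiating subjects in protocol 3.1.2 cover safety and efficacy, not exposure.

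**Stronger inferences.** A reader might quote a fixed range such as 14% to 36%. Its ends follow from assumed lengths (104/26/52 and 40/52/52 weeks) and are not bounds. A reader might also infer that the best responders will look least compliant, but subjects with stable disease may restart too. Nor does the SAP say that relative dose intensity is its test of whether the dose could be delivered.

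**Conclusion.** The point holds as a mismatch within SAP 7.4.1. For retreated monotherapy subjects the planned off-drug gap enters the denominator, so duration of therapy is overstated (by about 52 weeks at the maximum) and dose intensity and relative dose intensity are understated.

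The only size tied to documented limits is about 25%, or 23.5% with the last dosing intervals counted. It assumes that all three periods are at their maxima and that every dose is given. Actual values depend on gap and course lengths that the documents do not give, and the number of retreated subjects is not stated, so the effect on any summary statistic cannot be estimated.

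The matter is minor. It is confined to descriptive exposure summaries and listings. The primary safety endpoints in SAP 4.1 do not use these quantities, and the other cohorts are not affected.

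**What to change.** In SAP 7.4.1, for monotherapy subjects who re-initiate, compute duration, cumulative dose, dose intensity and relative dose intensity separately for the initial course (first dose to last dose before entering follow-up) and the retreatment course. If one total per subject is wanted, use the sum of the two on-drug course durations as the denominator. If a rule to this effect already exists in conventions not shown here, a cross-reference is enough.

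The cost is a sentence or two in the SAP and a course flag in the exposure dataset. No new data are needed.
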